8.3.1 Assessment of Adverse Events and Serious Adverse Events

The investigator is responsible for the detection and documentation of events meeting the criteria and definition of an AE or SAE described previously. At each visit, the subject will be allowed time to spontaneously report any issues since the last visit or evaluation. The investigator will then monitor and/or ask about or evaluate AEs using nonleading questions, such as

- * "How are you feeling?"
- * "Have you experienced any issues since your last visit?"
- * "Have you taken any new medications since your last visit?"

Any clinically relevant observations made during the visit will also be considered AEs.

8.3.2 Assessment of Intensity

The Investigator will make an assessment of intensity for each AE and SAE reported during the study, using his or her clinical judgment. The intensity of each AE and SAE recorded on the CRF should be assigned to one of the following categories:

- **Mild**: An event that is easily tolerated by the subject, causes minimal discomfort, and does not interfere with everyday activities
- **Moderate**: An event that is sufficiently discomforting to interfere with normal everyday activities
- **Severe**: An event that prevents normal everyday activities

An AE that is assessed as severe should not be confused with an SAE. *Severity* is a term used to describe the intensity of a specific event, and both AEs and SAEs can be assessed as severe. The event itself, however, may be of relatively minor medical significance (such as a severe headache). This is not the same as *serious*, which is based on the subject's or event's outcome or on action criteria usually associated with events that pose a threat to a subject's life or functioning (see Section 8.2).

Confidential Page 43 of 67

8.3.3 Assessment of Causality

The Investigator is obligated to use his or her clinical judgment to assess the relationship between the study medication and the occurrence of each AE or SAE. The Investigator will assess the relationship to the study medication by using the following criteria:

- **Definitely Related**: An AE has a strong temporal relationship to the study drug. The AE is most likely explained by study drug. Dechallenge and rechallenge (if possible) are positive. The AE is consistent with a known response to the study drug. Another etiology is unlikely or significantly less likely
- **Probably Related**: An AE has a strong temporal relationship to the study drug. The AE is more likely explained by study drug than by another cause. Dechallenge (if performed) is positive
- **Possibly Related**: An AE has a reasonable temporal relationship to study drug. The AE could have been due to another equally likely cause; dechallenge is positive
- **Not Related**: The subject did not receive the study drug **OR** the AE has no temporal relationship to study drug **OR** the AE has a much more likely alternate etiology **OR** the AE is due to an underlying or concurrent illness or effect of another drug

Even in situations in which minimal information is available for the initial SAE report, it is important that the Investigator always makes an assessment of causality for every event before transmitting the SAE reporting form and AE CRF page(s) to the Sponsor. The causality assessment is one of the criteria used when determining regulatory reporting requirements. The Investigator may change his or her opinion of causality in light of follow-up information and amend the SAE reporting form and AE CRF page(s) accordingly.

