8.2.2 Serious Adverse Events That Occur After Study Completion

If the Investigator becomes aware of an SAE or death that occurs in a subject within 30 days after Visit 4and that Investigator considers the event to be related to the study medication, the Investigator is obligated to report the SAE to the Sponsor.

Confidential Page 42 of 67

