8.3 Collecting, Recording and Evaluating Adverse Events and Serious Adverse Events

The AE reporting period for this study begins at Screening and ends at Visit 4. All AEs that occur in trial subjects during this reporting period must be reported, without consideration to drug relatedness. In addition, any known AE that occurs subsequent to the AE reporting period that the investigator assesses as related to the study medication should also be reported as an adverse event.

The Investigator will attempt to establish a diagnosis of the event on the basis of signs, symptoms, or other clinical information. In such cases, the diagnosis, not the individual signs or symptoms, should be documented as the AE or SAE. AEs will be collected from the point the ICF is signed through EOT or Early Termination Visit.

Both total and treatment-emergent AEs will be reported. Treatment-emergent AEs are defined as those that occur after dosing of study medication until EOT or Early Termination Visit.

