Any SAE that occurs during the study should be recorded by each clinical site and reported to the Sponsor Premier Research Pharmacovigilance.

SAEs considered definitely, probably, or possibly related to study drug shall also be classified by the Sponsor as being "expected" or "unexpected." An unexpected event is one that is not listed in the Investigator's Brochure.

The person responsible for the study shall ensure the study has been carried out in accordance with local pharmacovigilance regulations. All serious events reporting by Sponsor will adhere to 21 CFR 312.32 for IND drugs (7-day or 15-day alerts). Unexpected fatal or life-threatening SAEs considered related to the study drug should be reported to the FDA by the Sponsor with an Investigational New Drug (IND) Safety Report within 7 days. The Institutional Review Board (IRB) will be notified of the alert reports per FDA regulations.

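### 'Possibly Related' demands a positive dechallenge without exception, so an ambiguous adverse event with no dechallenge fits none of the four causality categories

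*Combined protocol and SAP*

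**What the plan says.** Section 8.3.3 first appeals to judgment: "The Investigator is obligated to use his or her clinical judgment to assess the relationship". It then prescribes the method: "The Investigator will assess the relationship to the study medication by using the following criteria". Four categories follow, and the three related ones treat dechallenge differently:

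- 'Definitely Related': "Dechallenge and rechallenge (if possible) are positive".
- 'Probably Related': "Dechallenge (if performed) is positive".
- 'Possibly Related': "The AE could have been due to another equally likely cause; dechallenge is positive".

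'Not Related' does not mention dechallenge. The section also wants a causality rating for every event before the SAE form is sent, even when little is known, and lets the investigator revise it as follow-up arrives.

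The rating is used later. Section 8.6 says "SAEs considered definitely, probably, or possibly related to study drug shall also be classified by the Sponsor" as expected or unexpected. Under Section 8.2.2, an SAE or death after study completion must be reported if the "Investigator considers the event to be related to the study medication". Under Section 8.3, a known AE after the reporting period that "the investigator assesses as related to the study medication should also be reported as an adverse event".

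**The concern.** A causality scale should ask for less evidence as it moves from stronger to weaker categories. Here the order is reversed between 'Probably' and 'Possibly' on one condition. An investigator who follows the criteria literally would find 'Possibly Related' closed whenever there was no dechallenge to observe. That is an ordinary situation: Section 8.4 lists an unchanged dose among the actions taken for an AE. It also covers a fatal event, which cannot show recovery on withdrawal, and an event that begins after dosing has ended.

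At stake are the consistency of ratings across sites and the few procedures that turn on whether an event is considered related. Some of these concern safety reporting to the sponsor and the regulator.

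**Working it through.** No arithmetic applies. The check applies the four definitions to one test event and then traces where the rating is used.

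**Test event.** Timing is reasonable, the drug and another cause are equally likely, and there is no dechallenge.

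| Category | Conditions in Section 8.3.3, paraphrased | Test event |
|---|---|---|
| Definitely | Strong timing; drug the most likely explanation; positive dechallenge and rechallenge, with an 'if possible' qualifier; known response; other cause unlikely | Fails: drug is not the most likely cause |
| Probably | Strong timing; drug more likely than another cause; positive dechallenge if one was done | Fails: drug is not the more likely cause |
| Possibly | Reasonable timing; another cause equally likely; positive dechallenge | Meets the first two, fails the third |
| Not Related | Any one of: drug not received; no link in time; a much more likely alternative; due to another illness or drug | Fails all: drug taken, timing reasonable, alternative only equally likely and not established |

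No category is satisfied.

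**Limits of the gap.** Change one feature at a time:

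- With strong timing and the drug more likely, the event is 'Probably Related' without any dechallenge.
- With a much more likely alternative, it is 'Not Related'.
- With a positive dechallenge, it is 'Possibly Related'.

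The gap is therefore mainly events that have an equally likely alternative and no dechallenge.

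The comparison rests on 'Probably Related'. In 'Definitely Related' the words 'if possible' may qualify rechallenge alone, so that category is not clear evidence either way.

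**Steps that use relatedness.**

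1. Section 8.6: the 7-day IND safety report covers unexpected fatal or life-threatening SAEs considered related.
2. Section 8.6: the sponsor's classification as expected or unexpected is stated for SAEs in the three related categories.
3. Section 8.2.2: the duty to report an SAE or death within 30 days after Visit 4 depends on the investigator considering it related.
4. Section 8.3: the same applies to a known AE after the reporting period.
5. Section 9.3.6.1: treatment-emergent AEs are tabulated by relationship.

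**Steps that do not use relatedness.**

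1. Section 8.6: every SAE or death during the study goes to the sponsor within 24 hours, whatever its cause.
2. Section 8.3: every AE in the reporting period is reported, whatever its cause.
3. Sections 9.3.6 and 9.3.6.1: safety data are summarised by treatment group and all AEs are listed.
4. Section 9.3.6.1: all SAEs are evaluated as possible unexpected adverse reactions. This is a backstop for the second step in the list above.

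**The case against.** The best defence is that Section 8.3.3 puts clinical judgment first, requires a rating when information is minimal and allows later revision. A rating that must be given before any dechallenge result can exist fits poorly with reading dechallenge as an absolute bar. Many investigators would choose 'Possibly Related' anyway. For SAEs, follow-up continues until resolution or stabilisation (Sections 8.3.4 and 8.5), so dechallenge information may arrive later. Sections 8.2.2 and 8.3 ask only whether the investigator considers the event related and do not cite the dechallenge clause. All of this stands and reduces the practical effect. It does not remove the inconsistency: a criterion that has to be overridden to give a sensible answer can be overridden differently by different raters.

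Three stronger readings are tempting, and the documents do not support them.

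- **Ambiguous events are pushed into 'Not Related', so harm is understated.** The test event fails that category too, and nothing in Section 8.3.3 sends it there. The result is a gap. A downgrade is possible but not prescribed.
- **Only SAEs rated related are ever assessed for unexpectedness.** Section 8.6 read alone suggests this, but Section 9.3.6.1 has all SAEs evaluated.
- **Planned completion measures the problem.** Section 9.1 plans 92 completers of 108 enrolled (92/108 = 85%), and one might infer that the category is closed for most AEs in 85% of subjects. That figure pools both arms, placebo included. It counts subjects, and says nothing about how many AEs have an equally likely alternative and no dechallenge.

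**Conclusion.** The inconsistency is real and follows from the text alone. 'Possibly Related' has a stricter dechallenge condition than 'Probably Related', and a definable class of events fits no category although each must be rated. Ratings in that class may be inconsistent, and some may come out as 'Not Related'.

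The effect is confined to the 7-day IND report, post-study and post-period reporting, and the by-relationship tables. The randomised comparison of all AEs does not use the rating. Sample size, power and type I error are untouched. The documents give no basis for counting the affected events. The conclusion assumes that at least some investigators apply the listed criteria as written; where judgment overrides them, the effect is smaller.

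**What to change.** In Section 8.3.3, replace the last clause of 'Possibly Related' with the protocol's own wording for 'Probably Related', "Dechallenge (if performed) is positive", so that missing dechallenge information no longer excludes the category. The test event then meets 'Possibly Related', because its other two conditions are already satisfied. If the form completion guides, which are not among the documents, repeat the definition, they should carry the same words.

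The cost is one phrase in the protocol. The downside is that a few more AEs will be rated related, and possibly a few more SAEs will need an expedited-reporting assessment.

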8.3.4 Assessment of Outcome

All SAEs must be followed until they are resolved, the condition stabilizes, the events are otherwise explained, or the subject is lost to follow-up. The Investigator will assess the outcome of the event by using the following terms:

- Resolved: The event resolved or the subject recovered without sequelae. An event (either serious or non-serious) occurred and had an endpoint, and the subject experienced no restrictions. Examples include stent placement for coronary artery disease (a device implanted is not a sequelae), an appendectomy (a scar is not a sequelae), a post-operative wound infection, or an upper respiratory tract infection
- Resolved with sequelae: The event has at least 1 secondary outcome that may result in permanent disability, functional limitation, or both. Such sequelae are usually limited to SAEs. Examples include hip replacement resulting in foot drop (foot drop is not the intended outcome but is a risk of surgery), stroke resulting in paralysis, or emboli formation after a bacterial infection resulting in a renal infarct and loss of renal function
- Resolving
- **Not resolved**: At the end of the study, an event either has not changed in intensity or may not have recovered to baseline values, and the outcome is unknown.

Confidential Page 44 of 67

- **Unknown**: The subject has withdrawn from the study prematurely or is lost to follow-up, and the status of the event is unknown
- Death

8.4 Documentation

All AEs that occur within the period of observation for the study must be documented in the CRF with the following information, where appropriate. (The period of observation for the study is described in Section 11.2.)

- AE name or term
- When the AE first occurred (start date and time)
- When the AE stopped (stop date and time or an indication of "ongoing")
- Severity of the AE
- Seriousness (hospitalization, death, etc.)
- Actions taken; may consist of:
 - O **Dose increased**: An indication that a medication schedule was modified by addition; either by changing the frequency, strength, or amount.
 - o **Dose not changed**: An indication that a medication schedule was maintained.
 - O Dose reduced: An indication that a medication schedule was modified by subtraction, either by changing the frequency, strength, or amount.
 - o **Drug interrupted:** An indication that a medication schedule was modified by temporarily terminating a prescribed regimen of medication.
 - o **Drug withdrawn**: An indication that a medication schedule was modified through termination of a prescribed regimen of medication.
 - o **Not applicable:** Determination of a value is not relevant in the current context.
 - o **Unknown**: Not known, not observed, not recorded, or refused.
- Outcome
- Investigator opinion regarding the AE relationship to the IP(s)

8.5 Follow-up of Adverse Events and Serious Adverse Events

Non-serious AEs will not be followed after the last scheduled study visit.

SAEs will be followed until the event resolves, the condition stabilizes, the event is otherwise explained, or the subject is lost to follow-up. The Investigator will make a reasonable attempt to obtain follow-up information and provide it to the Sponsor via Premier Research Pharmacovigilance. This includes results of any additional laboratory tests or investigations or consultations with other healthcare professionals that serve to clarify the nature of the event, the cause of the event, or both.

Confidential Page 45 of 67

New or updated information will be recorded on the originally completed SAE reporting form and CRF pages, with all changes signed and dated by the Investigator. The updated SAE reporting form and CRF pages should be resubmitted to the Sponsor via Premier Research Pharmacovigilance within the time frames outlined in Section 8.6. Investigators with subjects with unresolved SAEs at the time that the electronic database is to be closed will be informed and instructed how to make subsequent updates on the SAE to the Sponsor. The database will be locked and the data analyzed if unresolved SAEs remain. SAE updates will be reported to the Sponsor, to Regulatory Authorities, and IRBs within the timelines required by applicable regulations. All updates will also be filed in the Trial Master File retained by the Sponsor.

8.6 Prompt Reporting of Serious Adverse Events

Once the Investigator determines that an event meets the protocol definition of an SAE, he or she must notify the CRO within 24 hours, including weekends and holidays.

ANY SAE OR ANY OUTCOME OF DEATH DUE TO ANY CAUSE WHICH OCCURS DURING THE COURSE OF THIS STUDY, REGARDLESS OF RELATIONSHIP TO STUDY MEDICATION, MUST BE REPORTED TO THE SPONSOR IMMEDIATELY (WITHIN 24 HOURS).

Complete the SAE Reporting Form and forward by e-mail or fax to Premier Research Pharmacovigilance:

Table 7 Contact Information for SAE Reporting

What	Email	Phone/ Fax
24 Hour US Contact	[contact]	[contact]

E-mail transmission is the preferred method to transmit SAE information. In rare circumstances, and in the absence of e-mail capacity, notification by fax is acceptable

If the Investigator does not have all information regarding an SAE, he or she must not wait to receive additional information before notifying the CRO of the event. The form must be updated when additional information is received. Follow-up information received on all SAEs must be forwarded to the CRO by using the same procedure and timelines as for an initial report.

Within 24 hours after a SAE detection, observation, or report of occurrence (regardless of the relationship to test article), the investigator/qualified designee will complete a paper SAE Report Form with required information regarding the SAE and submit the completed form to Premier Research Pharmacovigilance. The data will also be entered into the appropriate module of the electronic data capture (EDC) as soon as possible after the paper form is sent to Premier Research Pharmacovigilance.

These SAE reports must contain the following information:

- 1. Study name/number
- 2. Study drug

Confidential Page 46 of 67

- 3. Investigator details (name, phone, fax, e-mail)
- 4. Subject number
- 5. Subject demographics
- 6. Clinical event
- 7. Description
 - a. Date of onset
 - b. Treatment (drug, dose, dosage form)
 - c. AE relationship to study drug
 - d. Action taken regarding study drug in direct relationship to the AE
 - e. Criteria for "Serious" applicable to the AE
- 8. Cause of death (whether or not the death was related to study drug)
- 9. Autopsy findings (if available)
- 10. Date of firs dose of Investigational Product
- 11. Date of last dose of Investigational Product, if applicable

Any SAE that occurs during the study should be recorded by each clinical site and reported to the Sponsor Premier Research Pharmacovigilance.

SAEs considered definitely, probably, or possibly related to study drug shall also be classified by the Sponsor as being "expected" or "unexpected." An unexpected event is one that is not listed in the Investigator's Brochure.

The person responsible for the study shall ensure the study has been carried out in accordance with local pharmacovigilance regulations. All serious events reporting by Sponsor will adhere to 21 CFR 312.32 for IND drugs (7-day or 15-day alerts). Unexpected fatal or life-threatening SAEs considered related to the study drug should be reported to the FDA by the Sponsor with an Investigational New Drug (IND) Safety Report within 7 days. The Institutional Review Board (IRB) will be notified of the alert reports per FDA regulations.

8.7 Regulatory Reporting Requirements for Serious Adverse Events

The Investigator must promptly report all SAEs to the CRO or designee in accordance with the procedures detailed in Section 8.6, "Prompt Reporting of Serious Adverse Events".

The Investigator, or responsible person according to local requirements, must comply with requirements related to the reporting of SAEs to the IRB. The Sponsor is responsible for reporting to Regulatory Authorities.

8.7.1 Procedures for Reporting Pregnancy Exposure and Birth Events

Should a female subject, or a male subject's partner become pregnant or be suspected of being pregnant while participating in this study, the event must be reported to the Sponsor upon receipt of information by the study staff. While the pregnancy itself is not considered to be an AE or a SAE, any pregnancy

Confidential Page 47 of 67

complications will be recorded as AEs or SAEs (if applicable). Pregnancy must be reported within 24 hours from first knowledge to the Sponsor via Premier Research Pharmacovigilance in writing via the Pregnancy Data Collection Form. This form shall be forwarded by e-mail or fax to the contacts details in Section 8.6.

Any pregnancy will be followed through to delivery for the observation of any SAEs including congenital abnormalities. Fatalities and spontaneous abortions must be reported as SAEs.

8.7.2 Overdose

The maximal dose of Investigational Product (20 mg) should not be exceeded during the study. Overdose that occurs during the study will be treated and documented as an AE/UAE/SAE if it fulfills the criteria. If the overdose does not result in an AE, it should be documented in the CRF. If the overdose does result in an SAE, it should be documented in the CRF and reported via a completed the SAE Reporting Form which is forwarded by e-mail or fax to Premier Research Pharmacovigilance The information contained therein should include study site identification, reporter identification, subject identification, Investigational Product, dose, action taken (e.g., administration of antidote <if available> or supportive measures or therapy), and any comments.

Confidential Page 48 of 67

9 STATISTICAL CONSIDERATIONS

This is a phase 3 randomized, double-blind (DB), placebo-controlled, parallel, study to assess the efficacy and safety of AMPH ER TAB compared to placebo for the treatment of ADHD in adults aged 18 to 60 years. The objective of the statistical analysis will be to evaluate the efficacy and safety of AMPH ER TAB compared to placebo in adult patients with ADHD aged 18 to 60 years.

All continuous study assessments will be summarized by treatment and time point using descriptive statistics (n, mean, median, standard deviation, minimum, and maximum). All categorical study assessments will be summarized by treatment and time point using frequency counts and percentages. Hypothesis testing, unless otherwise indicated, will be two-sided and performed at the 0.05 significance level.

A detailed statistical analysis plan (SAP) will be written and finalized prior to unblinding of the data.

